7. Investigator judges the subject to be an appropriate candidate for histology collection procedures (i.e. excision or biopsy);
8. Female subjects, must meet one of the following criteria with respect to their reproductive capacity:
 - a. Post-menopausal as defined by spontaneous amenorrhea for more than 12 months or spontaneous amenorrhea for 6-12 months with FSH level >40 mIU/mL;
 - b. Surgically sterile due to absence of ovaries or due to bilateral tubal ligation/occlusion performed more than 3 months prior to Screening;
 - c. Subject agreement to avoid pregnancy for one month after last dose (Week 12 or Week 40);
 - d. Women of Child Bearing Potential (WOCBP) are willing to use a contraceptive method with a failure rate of less than 1% per year when used consistently and correctly from Screening until one month following the last dose of investigational product (Week 12 or Week 40). The following are acceptable methods:
 - i. Hormonal contraception: either combined progestin-alone including oral contraceptive, injectable, implants, vaginal ring, or percutaneous patches. Hormonal contraceptives must not be used in subjects with a history of hypercoagulability (e.g. deep vein thrombosis, pulmonary embolism);
 - ii. Abstinence from penile-vaginal intercourse when this is the subject's preferred and usual lifestyle;
 - iii. Intrauterine device or intrauterine system;
 - iv. Male partner sterilization at least 6 months prior to the female subject's entry into the study, and this male is the sole partner for that subject;
9. Men who would father a child must agree to use at least one form of birth control during or continued abstinence from heterosexual intercourse prior to the study, for the duration of study participation and one month after completion of VGX-3100 administration;
10. Normal Screening electrocardiogram (ECG) or Screening ECG with no clinically significant findings as judged by the Investigator

^a An HIV rapid test may be used given the following conditions are met: 1. The test is an antigen/antibody immunoassay, 2. The test is only done using blood, 3. The test must be performed in the office and done by qualified study staff members

Exclusion:

1. Untreated micro invasive cancer^a;
2. Biopsy-proven Vaginal Intraepithelial Neoplasia (VAIN) and are not undergoing medical care and/or treatment for VAIN^b;
3. Biopsy-proven Vulvar Intraepithelial Neoplasia (VIN) and are not undergoing medical care and/or treatment for VIN^b;

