4.0 TRIAL POPULATION

4.1 INCLUSION CRITERIA

1. Must understand, agree and be able to comply with the requirements of the protocol and be able to provide voluntary consent to participate and sign an Informed Consent Form (ICF) prior to study-related activities;
2. Age 18 years and above;
3. Negative screening test for HIV-1/2^a within 30 days of Dose 1;
4. Confirmed anal or anal/peri-anal HPV-16/18 infection at Screening by PCR from HSIL specimen;
5. Anal tissue (blocks only) provided to the Study PAC for diagnosis must be collected within 10 weeks of first dose of VGX-3100;
6. At least one anal or anal/peri-anal (AIN2/3 and/or PAIN2/PAIN3) lesion that is histologically-confirmed as HSIL by the PAC at Screening;
 - i. The lesion needs to be large enough to biopsy, but the biopsy ($\geq 4\text{mm}$) should not remove the entire lesion in order to allow for continued lesion measurement while on the study;
7. Investigator judges the subject to be an appropriate candidate for histology collection procedures (i.e. excision or biopsy);
8. Female subjects, must meet one of the following criteria with respect to their reproductive capacity:
 - i. Post-menopausal as defined by spontaneous amenorrhea for more than 12 months or spontaneous amenorrhea for 6-12 months with follicle-stimulating hormone (FSH) level $>40\text{mIU/mL}$;
 - ii. Surgically sterile due to absence of ovaries or due to a bilateral tubal ligation/occlusion performed more than 3 months prior to Screening;
 - iii. Subject agreement to avoid pregnancy one month after last dose of IP (Week 12 or Week 40);
 - iv. Women of Childbearing Potential (WOCBP) are willing to use a contraceptive method with failure rate of less than 1% per year when used consistently and correctly from Screening until one month following the last dose of IP (Week 12 or Week 40). The following are acceptable methods:
 1. Hormonal contraception: either combined or progestin-alone including oral contraceptives, injectable, implants, vaginal ring, or percutaneous patches. Hormonal contraceptives must not be used in subjects with a history of hypercoagulability (e.g. deep vein thrombosis, pulmonary embolism);
 2. Abstinence from penile-vaginal intercourse when this is the subject's preferred and usual lifestyle;
 3. Intrauterine device or intrauterine system;

4. Male partner sterilization at least 6 months prior to the female subject's entry into the study, and this male is the sole partner for that subject;

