9. Men who could father a child must agree to use at least one form of birth control during or continued abstinence from heterosexual intercourse prior to the study, for the duration of study participation and one month after completion of VGX-3100 administration;
10. Normal Screening electrocardiogram (ECG) or Screening ECG with no clinically significant findings as judged by the Investigator

^a An HIV rapid test may be used given the following conditions are met: 1. The test is an antigen/antibody immunoassay, 2. The test is only done using blood, 3. The test must be performed in the office and done by qualified study staff members

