4.3.2 CRITERIA FOR WITHDRAWAL FROM STUDY

Subjects who become ineligible to continue on the study based on no longer meeting the inclusion criteria should be discontinued from study treatment and managed per routine standard of care but should continue on the study without further biopsy.

Should a subject fail to attend the clinic for a required study visit, the site should attempt to contact the subject and reschedule the missed visit as soon as possible. The site should also counsel the subject on the importance of maintaining the assigned visit schedule for follow-up and treatment of anal or anal/peri-anal HSIL, and ascertain whether or not the subject wishes to and/or should continue in the study based on previous noncompliance. In cases where the subject does not return for the rescheduled visit or cannot be reached to reschedule the missed visit, the site should make every effort to regain contact with the subject (3 telephone calls to the subject should be made and if that fails, then a certified letter is sent to the subject's last known mailing address) so that they can be considered withdrawn from the study for disposition purposes. These contact attempts should be documented in the subject's medical record. Should the subject continue to be unreachable, then and only then will the subject be considered to have withdrawn from the study with a primary reason of "Lost to Follow-up." For all other subjects withdrawing from the study, an alternative reason for discontinuation should be recorded in the eCRF.

If a subject elects to discontinue treatment/EP they should be encouraged to stay in the study and complete all follow-up visits and procedures and have all scheduled immune assessment blood samples collected as indicated in the Schedule of Events ([Table 8](#)). At a minimum, the Investigator should make every effort to have the subject complete all assessments designated for the discharge visit (Week 88). A subject will be considered to have completed the study when he/she completes all scheduled study treatments and follow-up visits.

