6.22 RESTRICTIONS

Subjects should not use alcohol or drugs that would interfere with study requirements during the course of the study and should report ALL medications/drugs, including illicit drugs, taken to the Investigator and/or other study personnel. To remain in the study, illicit drugs should not be taken.

Subjects should refrain from becoming pregnant until one month following the last dose of IP (Week 12 or Week 40) by using appropriate contraceptive measures (See Inclusion Criteria, Section 4.1). Lapses in contraceptive use should be reported to investigator and/or other study personnel.

Subjects should abstain from sexual activity and refrain from the use of douching and vaginal and anal lubricants/medication for a period of 24 hours prior to collection of ThinPrep™ samples.

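### Inclusion criterion 8 lets a woman of childbearing potential qualify on an agreement to avoid pregnancy alone, so the highly effective contraception in item iv is not an entry condition

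*Protocol*

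**What the plan says.** Section 4.1, criterion 8, begins "Female subjects, must meet one of the following criteria with respect to their reproductive capacity". Its four items are:

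- **i.** post-menopausal, as defined there;
- **ii.** surgically sterile, as defined there;
- **iii.** an undertaking, worded "Subject agreement to avoid pregnancy one month after last dose of IP (Week 12 or Week 40"), with no method attached to it;
- **iv.** the contraception requirement, which opens with "Women of Childbearing Potential (WOCBP) are willing to use a contraceptive method with failure rate of less than 1% per year when used consistently"; it applies over the whole period between Screening and a month past the final dose, and four acceptable methods follow.

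The synopsis has the same lead-in and the same order. Its item c reads "Subject agreement to avoid pregnancy for one month after last dose (Week 12 or Week 40"), again without a method. The contraception requirement is its item d, which begins "Women of Child Bearing Potential (WOCBP) are willing to use a contraceptive method with a failure rate of less than 1% per year". Version 2.0, which stands in the same file ahead of Version 3.0, has the same structure, so the amendment left it unchanged.

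Three other provisions bear on the point.

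- Section 6.22 tells subjects not to become pregnant before a month has passed since the final dose, and says this is to be done "by using appropriate contraceptive measures (See Inclusion Criteria, Section 4.1").
- Section 4.3.2 states: "Subjects who become ineligible to continue on the study based on no longer meeting the inclusion criteria should be discontinued from study treatment".
- Criterion 9, for men, begins "Men who could father a child must agree to use at least one form of birth control" and allows continued abstinence as the only other route.

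**The concern.** The lead-in makes the four items alternatives. That works for items i and ii, which are reproductive states. Items iii and iv both concern women who can conceive, and they read as two parts of one obligation: the undertaking and the means of keeping it. Joined by *one of*, the undertaking alone is enough. Item iv, with its threshold, its dated period and its list of methods, then screens out nobody who is prepared to give the undertaking.

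This is safety wording for an investigational DNA product in a trial that admits women of childbearing potential. Section 6.0 grants no waivers and has eligibility reconfirmed at every visit, so sites can be expected to apply the criteria as written. A site doing so under criterion 8 could accept a fertile woman who uses no listed method.

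**Working it through.** The protocol gives no figure to reproduce here. The check is one of logic, followed by a comparison of sections.

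**Step 1: criterion 8 as written and as evidently meant.** As written, the criterion is met if (i or ii or iii or iv). The reading that Section 6.22 presupposes is (i or ii or (iii and iv)). For a woman who is neither post-menopausal nor sterile, so that i and ii are false:

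| Woman | iii | iv | As written | i, or ii, or (iii and iv) |
|---|---|---|---|---|
| Agrees, will use a listed method | yes | yes | met | met |
| Agrees, no listed method | yes | no | **met** | **not met** |
| Neither agrees nor uses a method | no | no | not met | not met |

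The middle row is the defect.

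**Step 2: what item iii requires.** It names no method and no failure rate, and it gives no start at Screening. As worded, it speaks of the month after the last dose. Any female subject can give it.

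**Step 3: Section 6.22 against Section 4.1.** Section 6.22 expects contraceptive measures and refers to Section 4.1 for what they are. For women, the only measures listed there are those under item iv, which criterion 8 makes optional. The cross-reference therefore leads to a list that does not bind every woman it is meant to cover.

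**Step 4: lapses.** A woman who enters on item iv and then stops her method still meets criterion 8 through item iii. The Section 4.3.2 rule on subjects who cease to meet the inclusion criteria would not be triggered by that criterion.

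**Step 5: do other provisions restore item iv at entry?**

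- Criterion 1 requires agreement to comply with the protocol. Read with Section 6.22, it arguably excludes a woman unwilling to use any measure, but Section 6.22 states no failure rate.
- Exclusion 9 in Section 4.2 (10 in the synopsis) removes women who are pregnant or considering pregnancy within one month of the last dose. It does not ask for a method.
- Section 6.7.7 requires a negative urine test before each dose. Table 8 schedules tests at Screening, Day 0 and Weeks 4, 12, 15, 28, 36, 40, 64 and 88, which is 10 visits, with Week 40 needed only if a fourth dose is given. These tests detect pregnancy; they do not prevent it.
- Section 6.11 queries contraceptive compliance at each visit, and Section 7.10 stops dosing on pregnancy. Both act after entry.

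All of these lower the risk. None makes item iv a condition of eligibility.

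**The case against.** The strongest reply is that criterion 8 should not be read alone. Section 6.22 points to Section 4.1, and the only measures there for women are item iv's, so the pointer arguably imports that list as an on-study rule. Criterion 1 then makes willingness to follow it an entry condition. Item iv also names its own class, women of childbearing potential, and would have no function if item iii could replace it.

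Part of this stands. It shows that the intent can be recovered and that a careful site may well apply it. It does not settle the wording. Section 6.22 says *should*, gives no threshold, and defers to the very list whose connector is faulty. It is true that Section 4.3.2 also says *should*, so that verb alone is not decisive. The absent threshold and the circular reference carry more weight.

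Two further replies succeed in part. A lapse in contraception does not go unseen: Section 6.22 asks for it to be reported and Section 6.11 queries it. It merely fails to breach criterion 8. The contrast with men is also limited: criterion 9 gives them no lesser alternative, but it sets no failure rate and lists no methods, so it is not a stricter standard.

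A reader might infer two stronger claims, and the documents support neither.

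- **That Sections 4.1 and 6.22 contradict each other.** Neither permits what the other forbids. One governs entry and the other governs conduct on study and defers to the first.
- **That a period of dosing is left without any rule on pregnancy.** With Screening up to 10 weeks before Day 0, the time from Screening to the last dose is 12 + (0 to 10) = 12 to 22 weeks for three doses, or 40 + (0 to 10) = 40 to 50 weeks for four. Item iii does not name that time, but Section 6.22 covers everything up to one month after the last dose. Up to 10 weeks of each figure also precede any product, and the longer range applies only to partial responders given the optional fourth dose. The weeks describe item iii's wording, not time that the protocol leaves uncovered.

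**Conclusion.** The point holds as a drafting error in an operative eligibility rule. On its literal wording, criterion 8 admits a woman of childbearing potential on item iii alone, and no other provision makes the method with a failure rate below 1% per year an entry condition.

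Severity is minor. The intent is clear, several safeguards sit around the criterion, and sample size, power and the primary analysis are unaffected. The protocol does not state how many women could enter this way, so the size cannot be expressed as a count. The conclusion assumes that sites apply the connector as written; a site that reads items iii and iv together would see no practical difference.

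**What to change.** In Section 4.1 and the synopsis, recast criterion 8 as i, or ii, or (iii and iv), keeping the failure-rate threshold explicit. For example:

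*Female subjects must be (i) post-menopausal as defined, or (ii) surgically sterile as defined, or (iii) if of childbearing potential, agree both to avoid pregnancy and to use one of the listed contraceptive methods, with a failure rate below 1% per year under consistent and correct use, from Screening until one month following the last dose of IP (Week 12 or Week 40).*

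The list of methods stays as it is, including abstinence where that is the subject's usual lifestyle, and the pointer in Section 6.22 then works unchanged. If the consent form repeats the criterion, it needs the same sentence.

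The cost is a one-sentence amendment requiring IRB/EC approval (Section 9.5.6). The change does bind someone new: any woman admitted on item iii alone would have to start a listed method. Because eligibility is reconfirmed at each visit and Section 4.3.2 ties dosing to the inclusion criteria, the amendment should say how such women already enrolled are to be handled, so that dosing is not stopped unintentionally.

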4.2 EXCLUSION CRITERIA

1. Untreated micro invasive or invasive cancer^a;
2. Biopsy-proven Vaginal Intraepithelial Neoplasia (VAIN) and are not undergoing medical care and/or treatment for VAIN^b;
3. Biopsy-proven Vulvar Intraepithelial Neoplasia (VIN) and are not undergoing medical care and/or treatment for VIN^b;
4. Biopsy-proven Cervical Intraepithelial Neoplasia (CIN) 2/3 and are not undergoing medical care and/or treatment for CIN^b;
5. Biopsy-proven Penile Intraepithelial Neoplasia (PIN) and are not undergoing medical care and/or treatment for PIN^b;
6. Anal or anal/peri-anal HSIL that is not accessible for sampling by biopsy instrument;
7. Intra-anal and/or peri-anal lesion(s) that cannot be fully visualized at Screening; 8. Inability to have complete and satisfactory high resolution anoscopic exams (HRAs) as defined by full visualization of the anus, entire anal canal from the squamocolumnar junction at the border of the distal rectum, anal transformation zone, distal canal, anal verge, perianus;
8. Any treatment for anal or anal/peri-anal HSIL (e.g. surgery) within 4 weeks of Screening;
9. Pregnant, breast feeding or considering becoming pregnant within one month following the last dose of VGX-3100;
10. Presence of any abnormal clinical laboratory values greater than Grade 1 per Common Toxicity Criteria for Adverse Events (CTCAE) v4.03 within 45 days prior to Day 0 or less than Grade 1 but deemed clinically significant by the Investigator^c;
11. Immunosuppression as a result of underlying illness or treatment including:
 - a. Any prior history of other clinically significant immunosuppressive or clinically diagnosed Autoimmune disease;

- b. Any primary immunodeficiency;
 - c. Long-term use (≥ 7 days) of oral or parenteral glucocorticoids at a dose of ≥ 20 mg/day of prednisone equivalent (use of inhaled, otic, nasal, topical, and ophthalmic corticosteroids are allowed);
 - d. Current or anticipated use of disease modifying doses of anti-rheumatic drugs (e.g. azathioprine, cyclophosphamide, cyclosporine, methotrexate) and biologic disease modifying drugs such as Tumor Necrosis Factor (TNF)- α inhibitors (e.g. infliximab, adalimumab or etanercept);
 - e. Prior chemotherapy within 1 year;
 - f. History of solid organ or bone marrow transplantation;
12. History of previous therapeutic HPV vaccination (however, licensed prophylactic HPV vaccines are allowed, e.g. Gardasil[®]9, Gardasil[®], Cervarix[®]);
 13. Receipt of any non-study related non-live vaccine within 2 weeks before or after any VGX-3100 dose;
 14. Receipt of any non-study related live vaccine (e.g. measles vaccine) within 4 weeks before or after any VGX-3100 dose;
 15. Significant acute or chronic medical illness that could be negatively impacted by the electroporation treated as deemed by the Investigator;
 16. Current or history of clinically significant, medically unstable disease which, in the judgment of the investigator, would jeopardize the safety of the subject, interfere with study assessments or endpoint evaluation, or otherwise impact the validity of the study results (e.g. chronic renal failure, angina, myocardial ischemia or infarction, class 3 or higher congestive heart failure, cardiomyopathy, or clinically significant arrhythmias);
 17. Treatment for non-anogenital malignancy within 2 years of Screening, with the exception of superficial skin cancers that only require local excision;
 18. Bleeding or clotting disorder or use of blood thinners (e.g. anticoagulants or antiplatelet drugs) that would contraindicate IM injections within 2 weeks of a study dose;
 19. History of seizures unless seizure free to 5 years with the use of one or fewer antiepileptic agents;
 20. Sustained, manually confirmed, sitting systolic blood pressure >150 mm Hg or <90 mm Hg or a diastolic blood pressure >95 mm Hg at Screening or Day 0;
 21. Resting heart rate <50 beats per minute (bpm) (unless attributable to athletic conditioning) or >100 bpm at Screening or Day 0;
 22. Prior major surgery within 4 weeks of Day 0;
 23. Participated in an interventional study with an investigational compound or device within 4 weeks of signing the ICF (participation in an observational study is permitted);
 24. Less than two acceptable sites available for IM injection considering the deltoid and anterolateral quadriceps muscles;

- a. Tattoos, keloids or hypertrophic scars located within 2 cm of intended treatment site;
- b. Cardioverter-defibrillator or pacemaker on the ipsilateral side (to prevent a life-threatening arrhythmia) (unless deemed acceptable by a cardiologist);
- c. Metal implants or implantable medical device within the intended treatment site (i.e. electroporation area);

25. Any illness or condition that in the opinion of the Investigator may affect the safety of the subject or the evaluation of any study endpoint;

26. Vulnerable Populations:

- a. Drug (i.e. prescription or illicit) or alcohol use or dependence that, in the opinion of the Investigator, would interfere with adherence to study requirements;
- b. Prisoner or subject who is compulsorily detained (involuntary incarcerated) for treatment of either a psychiatric or physical (i.e. infectious disease) illness;
- c. Active military service personnel;
- d. Study-related staff or family members of study-related staff

^a This criterion includes subjects who have microscopic or gross evidence of invasive cancer, or the suspicion of cancer in any histopathologic specimen by any pathologist at screening.

^b When observation is the standard of care this will not exclude a subject from the study.

^c If the lab is redrawn and the result from the redrawn sample no longer meets this exclusion criteria, then the subject is not excluded on the basis of this criterion

4.3 DISCONTINUATION/WITHDRAWAL OF TRIAL SUBJECTS

4.3.1 CRITERIA FOR DISCONTINUATION FROM THE STUDY

Subjects who manifest a Grade 4 toxicity attributable to the study treatment will be discontinued from further treatment with VGX-3100. Subjects will not receive further doses of VGX-3100 followed by EP but will be encouraged to continue follow-up safety assessment through study discharge and not discontinue from the study.

If a subject manifests a Grade 3 toxicity attributable to VGX-3100/EP, the medical monitor and PI will discuss whether further treatment should be continued for that subject.

